9.3 Analysis Plan

We will follow these general analysis principles:

- The primary analyses will be performed according to the participant's assigned intervention.
- All participants who complete randomization and have surgery performed will be included in analyses.
- All events following surgery will be counted.
- All analyses will be conducted at the eye level, using the generalized estimating equations approach to correct standard errors (to account for the correlation between two eyes of a subject).
- Unless otherwise indicated, three sets of analyses will be performed: 1) BLTR 3 mm versus BLTR 5 mm and 2) BLTR 3 mm versus Trabut 3 mm 3) BLTR 5 mm versus Trabut 3 mm.

Post-operative Trichiasis Analyses:

The primary analyses will be based on the dichotomous outcome: presence or absence of post-operative trichiasis at any time point within 12-18 months following surgery. Both unadjusted and adjusted analyses will be performed. Adjusted analyses will account for the severity of pre-operative trichiasis, with severity defined based on the table below.

Trichiasis Severity Classification	Description
Mild	1-4 Eyelashes touching globe, no epilation OR 1-10 Eyelashes epilated, no eyelashes touching globe

Moderate	5-9 Eyelashes touching globe, no epilation OR 1-4 Eyelashes touching globe and 1-10 eyelashes epilated
Severe	5-9 Eyelashes touching globe and 1-10 eyelashes epilated OR 10+ Eyelashes touching globe, regardless of epilation status OR 11-20 Eyelashes epilated, regardless of eyelashes touching globe OR Entire eyelid epilated

(Gower et al. 2013. *JAMA Ophthalmol.*;131(3):294-301.)

Multiple secondary analyses of post-operative trichiasis will be performed. We will compare the severity of post-operative trichiasis between groups, with severity defined using the table above. First, we will compare the primary groups utilizing severity at first observation (6 weeks or 12 months for the primary outcome). Then we will compare groups using severity at final observation. This will allow us to determine whether one group has a higher ‘surgical failure’ rate and whether recurrent trichiasis progression varies across interventions. We will conduct both unadjusted and adjusted analyses.

Eyelid Contour Abnormalities:

Primary analyses of eyelid contour abnormalities will be based on a dichotomous variable: presence or absence of moderate/severe contour abnormality at the last study visit where the participant was seen between 6 weeks and 12-18 months, , or at last visit before repeat surgery using the photograph grade, which will be based on the definitions below. For the purposes of this analysis, mild will be combined with “no abnormality” and moderate and severe will be combined to form the “moderate/severe contour abnormality” group.

Abnormality	Definition
Mild	Vertical deviation from the natural contour, 1 mm in height (less than half the pupil height in daylight) and affecting 1/3 of horizontal eyelid length
Moderate	Vertical deviation from the natural contour 1–2 mm in height (about the pupil height in daylight) or affecting 1/3–2/3 of horizontal eyelid length
Severe	Vertical deviation from the natural contour 2 mm in height (more than the pupil height in daylight) or a defect >2/3 of the horizontal eyelid length

(Gower et al. 2012 *PLoS Negl Trop Dis* 6(6): e1713)

Secondary analyses will explore the relationship between incision height and the full range of eyelid contour abnormalities, which will require use of the photographic grade that will be graded centrally.

Targeted versus Actual Incision Height:

We will conduct an analysis to compare the assigned incision height against the actual incision height measured during surgery. If more than 10% of the heights vary by more than 0.5 mm, we will conduct secondary analyses for each of the above analyses to determine whether the results of the actual incision height analyses are similar to the per-protocol analyses. If differences exist, we will report these analyses separately, but will emphasize that the per-protocol analyses are the primary analyses.

New Versus Conversion Surgeons

Analyses will also be conducted stratifying based on surgeons' prior experience. Specifically, we will conduct all above analyses based on whether surgeons were trained on both bilamellar and Trabut simultaneously, or whether they first learned bilamellar and received additional training in Trabut at a later time.

1-day Surgical Corrections

Finally, we will conduct an analysis to determine whether there is a difference in the rate of 1-day surgical corrections by study arm.

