8 PROVISIONS FOR MONITORING STUDY PROGRESS	24
9 STATISTICAL CONSIDERATIONS	25
9.1 Study Hypotheses	25
9.2 Sample Size Considerations	26
9.3 Analysis Plan	27
10 QUALITY CONTROL AND QUALITY ASSURANCE	31

10.1	Training	31
10.2	Quality Monitoring	31
10.3	Data and Safety Monitoring Board	32
11	ETHICS/PROTECTION OF HUMAN SUBJECTS	33
11.1	Ethical Standards	33
11.2	Institutional Review Board.....	33
11.3	Informed Consent Process.....	33
11.4	Exclusion of Women, Minorities, and Children (Special Populations).....	33
11.5	Subject Confidentiality.....	34
12	COMMUNITY INVOLVEMENT PLAN.....	35
13	PUBLICATION/DATA SHARING POLICY	36

PROTOCOL SUMMARY

Title:

Evaluating the Role of Incision Height in Trichiasis Surgery Outcomes

Précis:

In this trial we will randomize 4,953 individuals with previously unoperated trichiasis on a 1:1:1 basis to bilamellar tarsal rotation trichiasis surgery with an incision height of 3mm, bilamellar tarsal rotation trichiasis surgery with an incision height of 5 mm, or Trabut surgery. Participants will receive trichiasis surgery and will be followed at 1 day, 2 weeks, 6 weeks, 12 months and 3 years after surgery. The primary outcome is development of post-operative trachomatous trichiasis (PTT) within 12-18 months after surgery. Logistic regression analyses will be performed to compare the rates of PTT in the 3 versus 5 mm incision BLTR groups, in the 3 mm BLTR versus Trabut group, and in the 5 mm BLTR versus Trabut group, adjusting for demographic characteristics and pre-operative trichiasis severity.

Objectives:

Primary objectives:

- 1) Examine whether the rate of post-operative trichiasis differs significantly for incisions placed 3 mm from the eyelid margin compared to incisions placed 5 mm from the eyelid margin.
- 2) Examine whether the rate of post-operative trichiasis differs significantly between surgery performed with the Trabut procedure versus bilamellar tarsal rotation with 3 mm incision height.
- 3) Examine whether the rate of post-operative trichiasis differs significantly between surgery performed with the Trabut procedure versus bilamellar tarsal rotation with 5 mm incision height.

[figure not shown]
Secondary objectives:

- 1) Determine whether the frequency of moderate/severe eyelid contour abnormalities differs following surgery performed with the bilamellar procedure when the target incision height is 3 mm versus 5 mm

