6.1 Eligibility Screening and Enrollment (Day 0)

Eligibility screening will take place at trichiasis surgery camps. Prior to this, local eye care workers will have identified all individuals with trichiasis and scheduled them for surgery. When patients present for trichiasis surgery, a trichiasis surgeon or screener will screen them for the presence of trichiasis and will note whether prior surgery has been performed on any eye that has trichiasis that day. Then the consent specialists will make a general announcement about the study and invite those who would like to learn more and possibly participate to meet individually with one of them.

The consent specialists will meet with trichiasis surgery patients in small groups to tell them about the study and then individually will assess eligibility using the Eligibility Review form. If they are eligible and interested in participating, the consent specialist will proceed to obtain informed consent with one patient at a time. The full process for

obtaining informed consent is provided in the Manual of Procedures. Those who provide consent will then meet with the project manager to be enrolled in the study.

Required Procedures/Data Collection:

- Complete Eligibility Screening form (Form 1)
- Obtain informed consent
- Collect Demographic and Tracking Information

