6.2 Baseline Ocular Exam and Surgery (Day 0)

The baseline exam occurs immediately after enrollment and just prior to surgery (all happen on the same day). The goal of this exam is to characterize trichiasis severity and visual acuity prior to surgery. Baseline trichiasis severity is an important predictor of post-operative trichiasis; hence, these data will be included in all models evaluating the outcome.

After the ocular exam, the patient receives trichiasis surgery.

Required Data Collection:

- Baseline Ocular Exam Form
- Surgical Evaluation Form

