9.2 Sample Size Considerations

The planned sample size for this trial is 4,953 participants. This sample size will give sufficient power to detect a 25% difference in post-operative trichiasis rates between 3 mm and 5 mm target incision heights for BLTR, a 25% difference in post-operative trichiasis rates for BLTR 3 mm versus Trabut and a difference of 25% between BLTR 5 mm and Trabut. This estimate is based on the following assumptions:

- 15% of eyelids in the BLTR 3 mm target height group will develop post-operative trichiasis during the 12 months following surgery
- Two-sided alpha error = 5%
- Power = 80%
- 40% of participants will have 2 eligible eyes
- The correlation between 2 eyes of an individual is 0.24
- 5% loss to follow up.

Based on these assumptions, the table below shows the total number of participants needed within the 3 arms combined.

Prevalence in control group	RR	Subjects per Arm	Total number of subjects In the 3 arms if 100% bilateral	Total number of surgeries needed	Only 40 % of surgeries will be bilateral # of surgeries	Additional Subjects (surgeries) to accrue the total number needed	Total number of subjects to be enrolled	Increase to account for 5% lost to follow-up
15%	0.70	743	2229	4458	3121	955 (1337)	3184	3351

16%	0.70	690	2070	4140	2898	887 (1242)	2957	3112
15%	0.75	1098	3294	6588	4612	1411 (1976)	4705	4953
16%	0.75	1019	3057	6114	4280	1310 (1834)	4367	4597

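### Does it matter that section 9.3 plans both an unadjusted and an adjusted analysis of post-operative trichiasis without saying which one decides?

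*Combined protocol and SAP*

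**What the plan says.** Under Post-operative Trichiasis Analyses, section 9.3 opens with "The primary analyses will be based on the dichotomous outcome". It then says "Both unadjusted and adjusted analyses will be performed" and describes the adjustment: "Adjusted analyses will account for the severity of pre-operative trichiasis, with severity defined based on the table below". The general principles at the head of 9.3 fix the rest of the model: participants are analysed as assigned, there are three pairwise comparisons, and "All analyses will be conducted at the eye level, using the generalized estimating equations approach to correct standard errors".

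Three other places bear on the point:

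- The Précis describes one analysis for all three comparisons, a logistic regression "adjusting for demographic characteristics and pre-operative trichiasis severity". It mentions no unadjusted analysis.
- Section 6.2, on the baseline examination, explains why severity is measured and adds "hence, these data will be included in all models evaluating the outcome".
- Section 6.1 lists "Collect Demographic and Tracking Information" among the enrolment procedures without naming variables.

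Section 9.1 states the three primary hypotheses and names no model. The sample size assumptions in section 9.2, such as "15% of eyelids in the BLTR 3 mm target height group will develop post-operative trichiasis during the 12 months following surgery", involve no covariate.

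**The concern.** Read alone, 9.3 seems to give each primary hypothesis two analyses of equal rank. If they fell on opposite sides of 5%, the sponsor could choose which one to present as the result. The two also estimate different quantities, because an odds ratio conditional on severity lies further from 1 than the crude one whenever severity predicts the outcome.

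Two details add to the impression. Section 6.2, taken literally, leaves no room for an unadjusted model. The Précis brings in demographic covariates that 9.3 does not mention and that are listed nowhere, so even the adjusted model seems to have two possible covariate sets. At stake would be the type I error of the three primary tests and the clarity of the headline estimate.

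**Working it through.** **The passages side by side.** In 9.3 the primary analyses are defined by their outcome. The statement that both versions will be run is a reporting convention: the same section repeats it for the secondary analyses of trichiasis severity. The Précis gives the form of the main comparison, which is adjusted. Section 6.2 describes a visit and is not a model specification; read as covering the adjusted models, it agrees with 9.3. All descriptions of the adjusted model include severity. They differ only on whether demographics are added.

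**Size: inputs.** From the documents: 4,953 participants, three equal arms, 5% loss, 40% bilateral, correlation between eyes 0.24, control rate 15%, relative risk 0.75 (so 11.25%), two-sided 5%.

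The later steps of the table in 9.2 reproduce:

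- 3 × 1,098 = 3,294 subjects, or 6,588 surgeries
- 6,588 × 0.7 = 4,612, leaving 1,976
- 1,976 / 1.4 = 1,411 more subjects, total 4,705
- 4,705 / 0.95 = 4,953

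The starting figure of 1,098 per arm does not follow from 5% and 80% power. Those inputs with a design effect of 1.24 give 789. That is a separate matter, but it explains why power below is above 80%.

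**Unadjusted power at the planned size.**

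- Evaluable per arm: 4,953 / 3 × 0.95 = 1,568 participants; × 1.4 = 2,196 eyes
- Design effect: 1 + 0.24 × (2.2 / 1.4 − 1) = 1.137, giving 1,931 effective eyes
- SE = √[(0.15 × 0.85 + 0.1125 × 0.8875) / 1,931] = 0.01085
- z = 0.0375 / 0.01085 = 3.46; power = Φ(3.46 − 1.96) ≈ 93%
- Crude odds ratio: (0.1125 / 0.8875) / (0.15 / 0.85) = 0.718

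**How far the analyses differ under the alternative.** The documents give no prognostic effects, so three strengths were assumed:

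- weak: severity mix 40/30/30%, risks 11/15/20.3%, demographic odds ratio 1.2 per SD
- moderate: 50/25/25%, 9/16/26%, 1.3
- strong: 50/25/25%, 6/15/33%, 1.5

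Simulation used 8,016 two-arm trials per setting and eye-level logistic GEE with robust errors. Both eyes were assumed to share severity.

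| | weak | moderate | strong |
|---|---|---|---|
| Mean OR, unadjusted | 0.718 | 0.717 | 0.718 |
| Mean OR, severity-adjusted | 0.715 | 0.709 | 0.695 |
| Mean OR, severity plus one demographic | 0.714 | 0.706 | 0.689 |
| Power, unadjusted | 93.4% | 93.7% | 93.2% |
| Power, severity-adjusted | 94.0% | 94.6% | 96.0% |
| Verdict differs, unadjusted vs severity | 1.2% | 2.1% | 3.9% |
| Verdict differs when demographic is added to severity | 0.9% | 1.0% | 1.4% |

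**Type I error if either analysis could count as a win.** This is the harm the concern implies. The SD of the difference in log odds ratio between the unadjusted and severity-adjusted estimates was 0.012, 0.021 and 0.034, against an SE of about 0.096. Assume bivariate normal test statistics and the same SDs under the null. The correlation is then 1 − ½(SD / SE)²:

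- 1 − ½(0.012 / 0.096)² = 0.992, giving 5.6%
- 1 − ½(0.021 / 0.096)² = 0.976, giving 6.0%
- 1 − ½(0.034 / 0.096)² = 0.937, giving 6.6%

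A second simulation had power near 80% (1,330 independent units per arm, severity mix 40/30/30%, severity odds ratio 1.5 to 3 per step, 4,000 runs per setting). Each analysis alone held 4.7% to 5.1% type I error, and either-wins gave 5.6% to 6.1%. Verdicts at relative risk 0.75 differed in 2.3% to 6.5% of trials.

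**The case for a change.** The best case for a change is that no passage calls the adjusted model the deciding one, and that 9.3, the operative section, places both versions ahead of its secondary analyses. The plan does rank analyses elsewhere: under Targeted versus Actual Incision Height it says which set is primary. With three comparisons the chances add up. In a three-arm simulation at assumed rates of 15%, 11.25% and 11.25%, at least one of the three verdicts differed between the two analyses in 4.0%, 6.5% and 8.9% of trials for weak, moderate and strong severity effects. A sentence of ranking would cost almost nothing.

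Part of this stands. The ranking is implied, not stated, and the demographic covariates are not named. But the freedom is narrower than it looks. Presenting only the unadjusted result would depart visibly from the Précis, and 9.3 commits the sponsor to running both, so a disagreement would be there to report. Adding a demographic covariate to severity changed the verdict in at most 1.4% of trials. The difference between crude and conditional odds ratios does not affect which null is tested: with randomised arms and no effect at any severity level, both equal 1. The literal conflict with 6.2 disappears once its sentence is read as describing the adjusted models.

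**Conclusion.** No change to the plan is called for. The text does leave out an explicit ranking and a list of demographic covariates, but this is detail that analysts can fill from the Précis, which describes an adjusted logistic regression for all three comparisons. Followed as written, the plan produces two valid as-assigned analyses of each hypothesis. A further sentence would mostly write down what the Précis already implies and would still leave the choice of demographics to the investigators.

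Under the assumed severity effects, odds ratios differ by 0.003 (0.718 vs 0.715) to 0.023 (0.718 vs 0.695). Verdicts per comparison differ in 1.2% to 3.9% of trials at about 93% power, and in 2.3% to 6.5% near 80% power. Type I error stays at about 5.6% to 6.6% per comparison even if either analysis could count as a win. These figures rest on severity mixes, risks and demographic effects that the documents do not give, and the larger simulation also assumes that both eyes share severity. Stronger prognostic effects would widen the gap.

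### Section 9.3 mislabels its as-assigned primary analyses as per-protocol, and its secondary actual-height analysis can be confounded by surgeon because no model includes surgeon

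*Combined protocol and SAP*

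**What the plan says.** The general principles in Section 9.3 state: "The primary analyses will be performed according to the participant's assigned intervention". They also fix the analysis set: "All participants who complete randomization and have surgery performed will be included in analyses".

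Later in Section 9.3, under Targeted versus Actual Incision Height, a conditional analysis is planned: "If more than 10% of the heights vary by more than 0.5 mm, we will conduct secondary analyses for each of the above analyses". Its purpose is to see whether the "results of the actual incision height analyses are similar to the per-protocol analyses". If they differ, the actual-height results are reported separately, and the authors "but will emphasize that the per-protocol analyses are the primary analyses".

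On covariates, Section 9.3 says "Adjusted analyses will account for the severity of pre-operative trichiasis". Section 6.2 says of baseline severity: "hence, these data will be included in all models evaluating the outcome". The Précis adds demographic characteristics. Surgeons appear in Section 9.3 only through stratification by training history (trained in both procedures together, or converted to Trabut later).

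**The concern.** There are two issues, both in the paragraph on off-target incisions.

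- **The label.** Per-protocol usually means that non-adherent cases are left out. Off-target incision height is the deviation for which an as-assigned and a per-protocol analysis would differ. An analyst who took the word literally could drop off-target eyelids from the primary analysis and cite Section 9.3 for doing so.
- **The surgeon.** The height actually cut is determined after randomisation, so grouping by it gives up the protection of randomisation. If surgeons differ both in how often they miss the target and in their recurrence rates, an actual-height comparison can show a difference that belongs to the surgeons. Section 2.1 says the 5 mm hypothesis itself came from scar-height associations within earlier trials. A second analysis of that kind should be labelled as such and adjusted for the obvious common cause.

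**Working it through.** **Step 1. Which meaning of per-protocol fits the text?** Three readings can be tested against the two general principles.

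- *Off-target eyelids excluded.* This contradicts the rule that all randomised and operated participants are analysed.
- *Off-target eyelids regrouped by height cut.* This contradicts analysis by assigned intervention. The planned check would also compare the actual-height analysis with itself.
- *As assigned.* This agrees with both principles, and with a paragraph that opens by setting assigned height against measured height.

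Only the third reading is consistent. No per-protocol population is defined anywhere in the documents, so there is nothing to implement under the first. The word is wrong, and it is used twice.

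**Step 2. Is surgeon dealt with in the actual-height analysis?**

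- Section 4.4.1: the operating team measures and records the height cut, in all three arms.
- Section 5.3: deviations above 0.5 mm are reported cumulatively by surgeon, and a surgeon with more than 5% of measurements off target is re-evaluated. The plan therefore allows for deviation rates that vary by surgeon.
- Précis and Sections 6.2 and 9.3: the covariates are demographics and baseline severity. Surgeon is not listed.
- Section 9.3: the generalized estimating equations handle two eyes of one person, not surgeons.
- Section 9.3: stratification by training history separates two kinds of surgeon. Surgeons within a stratum can still differ.

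Surgeon is a plausible common cause of off-target height and of outcome, and it is not adjusted for.

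**Step 3. Size.** Correcting the label changes no sample size, alpha or power. The documents give no number of surgeons, deviation rate or between-surgeon spread, so surgeon bias cannot be estimated. The following range is illustrative only.

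*From Section 9.2:* 15% recurrence, taken for both BLTR arms (no true height effect).

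*Assumed:* a group of surgeons performs 30% of eyelids in each arm. Their recurrence is r = 1.5 to 3 times that of the others, and they are k = 2 to 3 times as likely to miss. A fraction f = 10% to 20% of 3 mm eyelids miss and are all counted as 5 mm. No 5 mm eyelid misses.

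- Recurrence for the other surgeons: b = 0.15 / (0.7 + 0.3r)
- Miss rate for the other surgeons: q = f / (0.7 + 0.3k)
- Recurrence in missed eyelids: D = [0.3·kq·rb + 0.7·q·b] / f
- Recurrence in on-target eyelids: T = (0.15 − f·D) / (1 − f)
- Apparent risk ratio, 5 mm versus 3 mm: [(0.15 + f·D) / (1 + f)] / T

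| | f | r | k | b | q | D | T | Apparent RR |
|---|---|---|---|---|---|---|---|---|
| Low end | 0.10 | 1.5 | 2 | 0.1304 | 0.0769 | 0.1605 | 0.1488 | 0.1510/0.1488 = 1.01 |
| High end | 0.20 | 3 | 3 | 0.0938 | 0.1250 | 0.1992 | 0.1377 | 0.1582/0.1377 = 1.15 |

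If instead only 5 mm eyelids miss, the ratios invert to 1/1.01 = 0.99 and 1/1.15 = 0.87. If both arms miss equally and in the same pattern, both groups return to (1 − f)·T + f·D = 15% and the ratio is 1.00.

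The one-sided cases also sit awkwardly with the trigger. With equal arms, 20% misses in one BLTR arm is 20/2 = 10% of BLTR heights, or 20/3 = 6.7% across three arms. Neither is above 10%, so the analysis would run only if the trigger were read arm by arm, which Section 9.3 does not say. The illustration shows that the direction and size depend on inputs the documents do not give.

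**The case against.** The best defence is that nothing in the primary analysis is really open. Two explicit rules fix it, no rival set is defined, and the context shows what the word means. That stands, and it is why this is a wording correction. A reader might infer a second primary population, or a plan to discard off-target eyelids. The documents do not support either.

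A reader might also infer that the actual-height comparison is confounded by eyelid severity. No section links off-target incisions to severity, and baseline severity is already planned in the adjusted trichiasis models (Sections 6.2 and 9.3), which the actual-height work repeats. Only the unadjusted version and unmeasured lid features stay exposed.

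A reader might further infer a large false height effect. That needs misses in one direction, full regrouping of eyelids that may be little more than 0.5 mm off, and a deviation rate that may not meet the trigger, "If more than 10% of the heights vary by more than 0.5 mm". No such figure can be drawn from the documents.

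Other safeguards are real. The analysis is secondary, reported separately and subordinate to the primary. Its trigger depends on adherence, not outcome. Section 5.3 provides for corrective action with surgeons who drift. Stratifying by training history deals with part of the variation between surgeons. Running the analysis unconditionally, modelling height as continuous, or using assigned arm as an instrument would be design preferences, not corrections.

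What the defence does not answer is that the word contradicts the stated principle, and that surgeon is left out of an unrandomised comparison in a trial that monitors deviation by surgeon.

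**Conclusion.** The point holds in two limited parts.

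1. Section 9.3 twice gives the primary analyses a name that conflicts with its own rule. The conflict is one of terminology, and the as-assigned reading is the only one consistent with the rest of the section.
2. The secondary actual-height analysis is not protected by randomisation and can be confounded by surgeon. This rests on surgeons differing in both accuracy and recurrence rate. The documents make the first plausible and are silent on the second.

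The randomised comparisons are unaffected. No size should be attached to the surgeon bias: it may be nil, and its direction is unknown. The change is worth making because it is cheap and prevents a misreading of the trial's central question.

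**What to change.** In Section 9.3, under Targeted versus Actual Incision Height:

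- Replace per-protocol with assigned-intervention in both places, and keep the existing rule that everyone randomised and operated is analysed.
- Add individual surgeon to the planned severity-adjusted actual-height model.
- State that this adjusted version is the one to interpret.
- State that the comparison is observational, because actual height is determined after randomisation.

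The cost is two word changes, two sentences and one modified secondary model. No new data are needed: heights are recorded at surgery, and deviations are already reported by surgeon. With surgeon as a fixed factor, the model gains one parameter fewer than the number of surgeons, which the documents do not state. Intervals in that one secondary analysis become slightly wider. The primary analyses, sample size, alpha and power do not change.
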